Survival time will be evaluated by setting death as the event of interest. For patients who complete the study, survival status will be determined on the first follow-up date exceeding 3 years after the start of treatment with this drug at the own site. In the case of death, information on the cause, i.e., whether the death is due to TTR-FAP or to another cause (including unknown) will also be collected. *For patients who started the treatment with this drug after May 2018 (1.5-year observation period), their survival should be confirmed using the attached CRF* on the first follow-up date exceeding *1.5 years after the start of treatment at the own site.* 

The following two kinds of event will be evaluated:

- Death from any cause
- FAP-related death (Death from TTR-FAP is set as the event of interest. Death with missing cause will
  not be regarded as an event of interest.)

Time to event will be evaluated with respect to the following two kinds of time:

- Time from start of treatment to event
- Time from onset of FAP to event

CC				
I				
l				

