#### 7. HANDLING OF MISSING DATA

Adverse Events

If the severity of, action taken for, or outcome of an AE is missing, their value will be considered "unknown" for data summarizations.

– NIS

If the evaluation result for the right or left side on the same day is missing, the value for the evaluated side will be adopted as the score for the item.

– QOL-DN

If the score of an item included in the Physical Function/Large Nerve Fiber Disorder subscale, Activities of Daily Living subscale, Symptoms subscale, Small Nerve Fiber Disorder subscale, or Autonomic Neuropathy subscale is missing, the missing score will be imputed with the mean score from the evaluated items in the relevant subscale as long as  $\geq 60\%$  of the items in the subscale have been evaluated. The score for the subscale will be determined by summing the scores for the evaluated and imputed items.

The TQOL score will be determined by summing the scores for the evaluated and imputed items if all the 35 items have been evaluated or all missing values imputed by using the aforementioned method. If imputation could not be done by the aforementioned method for some items because of failure of evaluation for  $\geq 60\%$  of all items in a subscale, the TQOL score will be determined as 35 times the mean from the evaluated and imputed items, provided that at least 60% of all items have been evaluated or imputed. If  $\geq 40\%$  of the items in a subscale or the TQOL score are missing, the score for the subscale and the TQOL score will be treated as missing values.

Neurological Assessment

If the item toe extension and/or toe flexion in the motor domain have been evaluated and the results are directed to normal, other items in the same domain will be imputed with those directed to normal. If the item triceps surae in the reflexes domain has been evaluated and the result is normal, other items in the same domain will be imputed with normal. If the item toe in the light touch, pin prick, vibration, or position sense domain has been evaluated and the result is normal, other items in the same domain will be imputed with normal.

- Evaluation of Survival Time

If the cause of death is missing in the record of a death-confirmed patient, the patient will be treated as having died for unknown cause.

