#### 8.1.5. Time (to event) data

For time data containing right-censored data, Kaplan-Meier's method will be used to determine the median, 1st quartile, and 3rd quartile. Kaplan-Meier plots will also be presented, as necessary.

For time data containing interval censored data, the EMICM algorithm will be used to determine the median, 1st quartile, and 3rd quartile. Estimated survival plots will also be presented, as necessary. A reference program is shown in Section 10.3.1.

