## 8.2.4.6. Evaluation of survival time

Each time to each event  $(2 \times 2)$  noted in the evaluation of survival time in Section 6.2 will be analyzed as described in Section 8.1.5. Survival rates will also be calculated at 1.5 and 3 years for the time from the start of treatment to the event and at 10 and 20 years for the time from FAP onset to the event (enter NA if not estimable). When death related to FAP is an event, other deaths will be right-censored.

[figure not shown]
The outline of how to handle cases at the time of analysis in the evaluation of survival time is shown below.

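### The FAP-specific Kaplan-Meier rate is a net quantity, not one minus the probability of dying from FAP: other deaths are censored, and deaths of unknown or missing cause are counted as non-FAP with no visible sensitivity analysis

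*SAP*

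**What the plan says.** SAP 6.2 sets two events, death from any cause and FAP-related death, and two time origins, start of treatment and onset of FAP. For the second event, "Death from TTR-FAP is set as the event of interest".

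Three places settle what happens to the remaining deaths:

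- SAP 8.2.4.6: "When death related to FAP is an event, other deaths will be right-censored".
- SAP 6.2: the sentence opening "Death with missing cause will" goes on "not be regarded as an event of interest". The same section puts unknown causes with the non-FAP causes when it describes the information collected: "whether the death is due to TTR-FAP or to another cause (including unknown").
- SAP 7: where the cause is missing, "the patient will be treated as having died for unknown cause".

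The estimators are in SAP 8.1.5: "For time data containing right-censored data, Kaplan-Meier's method will be used", with EMICM where times are interval-censored. SAP 8.2.4.6 asks for survival rates at 1.5 and 3 years from treatment start and "at 10 and 20 years for the time from FAP onset to the event", marked NA if not estimable. The readable text names no competing-risk estimator, no sensitivity analysis on cause of death, and no delayed-entry rule for the onset scale.

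**The concern.** A patient who dies of another cause can no longer die of FAP. Treating that death as ordinary censoring assumes the patient keeps the same future risk of FAP death as those still alive. The resulting curve describes a setting in which other deaths do not occur. That is a legitimate net-survival summary, but its complement exceeds the actual proportion dying of FAP whenever any competing death occurs.

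The cause-of-death rule works the other way. Any true FAP death with unknown or missing cause becomes a censored observation, which can only lower the FAP figure.

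At stake is the reading of a descriptive output in the final analysis, which SAP 3 says supports the reexamination application. A FAP-specific rate printed beside the all-cause rate invites the reader to take its complement as FAP mortality.

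**Working it through.** The documents give no survival rate, death count or cause split, so there is no planned figure to reproduce. All hazards and shares below are assumptions.

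**1. Competing deaths only.** Let h1 be the FAP hazard and h2 the other-cause hazard, both constant, with complete follow-up from the time origin.

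- SAP quantity: 1 − KM(t) = 1 − exp(−h1·t)
- Probability of FAP death: CIF(t) = h1/(h1+h2) × [1 − exp(−(h1+h2)·t)]

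With h1 = 0.05, h2 = 0.02 and t = 20: 1 − exp(−1.0) = 63.2%, against (0.05/0.07) × [1 − exp(−1.4)] = 53.8%. The gaps below use unrounded values.

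| t (years) | 1 − KM | CIF, h2 = 0.01 / 0.02 / 0.03 | Gap (points) |
|---|---|---|---|
| 3 | 13.9% | 13.7 / 13.5 / 13.3% | 0.2 / 0.4 / 0.6 |
| 10 | 39.3% | 37.6 / 36.0 / 34.4% | 1.7 / 3.4 / 4.9 |
| 20 | 63.2% | 58.2 / 53.8 / 49.9% | 5.0 / 9.4 / 13.3 |

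**2. Adding the unknown-cause rule.** Protocol 5 gives survival of about 10 years after onset in the accumulated areas. Used only for scale, take that as an all-cause median of 10 years. Let p be the share of deaths not due to FAP, and u the share of FAP deaths with unknown or missing cause.

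- SAP quantity: 1 − 2^(−(1−p)(1−u)t/10)
- Probability of FAP death: (1−p) × (1 − 2^(−t/10))

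| p | u | 10 years: SAP vs true | 20 years: SAP vs true |
|---|---|---|---|
| 0 | 20% | 42.6 vs 50.0% | 67.0 vs 75.0% |
| 10% | 10% | 43.0 vs 45.0% | 67.5 vs 67.5% |
| 20% | 0 | 42.6 vs 40.0% | 67.0 vs 60.0% |
| 20% | 20% | 35.8 vs 40.0% | 58.8 vs 60.0% |
| 40% | 20% | 28.3 vs 30.0% | 48.6 vs 45.0% |

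The sign changes with the mix, and in one row the two effects cancel at 20 years. At 3 years the competing-death part is small but the unknown-cause part is not: with p = 0 and u = 20%, the figures are 15.3% vs 18.8%.

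A simulation of 200,000 patients with p = 30% and u = 0 confirms the mechanism. At 20 years, 1 − KM was 62.2%, Aalen-Johansen 52.5% and the truth 52.5%. The 1 − KM values for FAP and other deaths summed to 96.4%, against all-cause mortality of 75.1%.

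**3. Entry on the onset scale.** Step 1 assumes follow-up from onset. In this study patients enter at treatment start and are followed for up to 3 years (Protocol 7.2.4 and 7.3.2.13). A patient must therefore survive from onset to treatment to be seen at all. This was simulated with h1 = 0.05, h2 = 0.02, 3 years of follow-up, an assumed mean onset-to-treatment time of 3 to 8 years, and no delayed-entry adjustment.

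- 1 − KM at 20 years was about 34% to 53%.
- It exceeded Aalen-Johansen by 2.4 to 6.3 points, so Aalen-Johansen was about 32% to 47% (34 − 2.4; 53 − 6.3).
- Both were below the true 53.8%.

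A second run, with gamma-distributed delays (shape 2) averaging 3, 5 and 8 years, gave 49.8%, 39.5% and 27.3%, with gaps of 5.5, 3.4 and 1.6 points. The level depends on how the delays are modelled, but the pattern is the same. With delayed entry modelled, the 20-year gap returns to about 9 to 10 points.

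**The case against.** Cause-specific Kaplan-Meier is a recognised summary. The SAP calls its output a survival rate and never calls it a probability of FAP death. There is no hypothesis or decision rule (SAP 4.1 and 4.2). The cause-of-death rule is stated openly, and deaths and survival times are listed by patient (SAP 8.2.3.2 and 9). All of this stands, and it makes the point one of estimand and labelling. The rule still leaves the reader without the quantity most will look for.

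Four stronger readings are tempting, and the documents do not support them:

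- *The plan overstates FAP mortality.* The two rules oppose each other. On the onset scale, ignoring delayed entry put the 20-year figure below the truth in step 3.
- *Unknown-cause deaths are lost.* They are non-events only in the FAP-specific analysis. The all-cause analysis counts every death.
- *The figures will be set against natural history.* Neither document plans this. The only such figure, survival of about 10 years after onset in Protocol 5, concerns overall survival and would pair with the all-cause curve.
- *Switching to Aalen-Johansen makes the 10- and 20-year figures actual risks.* Step 3 shows that it does not unless entry is also handled.

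SAP 8.2.4.6 points to a case-handling figure that is not reproduced in the text available to us, and parts of the SAP are redacted. Delayed entry or a sensitivity analysis may be specified there. The written censoring rule holds either way.

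**Conclusion.** The point holds as a minor one. In the FAP-related-death analysis, one minus the reported rate is a net quantity and should not be read as the probability of dying from FAP. No net direction of error can be stated, and the all-cause results are untouched by either rule.

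The sizes in the working rest on constant hazards, assumed cause shares and, on the onset scale, assumed onset-to-treatment times. The competing-death effect is negligible at the planned treatment-start time points and matters mainly at 20 years from onset. The unknown-cause effect can matter at any time point. If every death were due to FAP with its cause recorded, both effects would be zero.

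**What to change.** In SAP 8.2.4.6 and 8.1.5:

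1. For FAP-related death, report Aalen-Johansen cumulative incidence, with other-cause death as a competing event, at 1.5 and 3 years from treatment start and at 10 and 20 years from onset.
2. Keep Kaplan-Meier for all-cause death. Label any FAP-specific Kaplan-Meier rate that is retained as net survival.
3. Repeat the FAP analysis once with deaths of unknown or missing cause counted as FAP-related. With the main analysis, this bounds the effect of the rule.
4. On the time-from-onset scale, enter patients into the risk set at treatment start (left truncation), unless the case-handling figure already specifies this. Without it, the 10- and 20-year figures stay biased under either estimator.

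The first three items use cause and date of death already collected under Protocol 7.3.2.13. Item 4 uses the onset and treatment-start dates. The cost is SAP wording, one extra curve, one sensitivity run, and a stated date convention (for example the midpoint) for any interval-censored deaths, which EMICM would otherwise handle.

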#### 8.2.4.7. Subgroup analyses

For the measured values of NIS-LL score and TQOL and the changes from the baseline at each time point in A1.1, summary statistics will be calculated for each factor specified in Section 5.4. For prior treatments and concomitant medications, whether to perform subgroup analysis for which treatment/medication will be examined prior to analysis and recorded in order to perform more appropriate evaluation.

#### 8.2.6. Pharmacokinetics

## 8.2.6.1. Measurement of plasma tafamidis concentrations in patients with severe hepatic impairment

If plasma tafamidis concentrations were measured in patients with severe hepatic impairment, they will be listed and compared with those previously obtained in healthy adults and subjects with moderate hepatic impairment (Study Fx1A-105).

#### 9. Listings

The following listings will be prepared:

- Patient listing
- List of mutant genotypes (patients diagnosed with mutant genotypes)
- List of patients with adverse reactions
- List of patients with adverse reactions excluded from safety analysis
- List of patients with serious adverse reactions
- List of patients with adverse reactions among patients with hepatic impairment
- List of patients with adverse reactions among patients with renal impairment
- List of elderly patients with adverse reactions
- List of pediatric patients with adverse reactions
- List of patients with adverse reactions among patients who became pregnant during the period from the start date of treatment to the end of the observation period (or the end date of the study)
- List of events corresponding to major investigation items
- List of patients with adverse reactions of major investigation items
- List of deaths

- List of adverse reactions in pregnant and parturient women
- List of adverse reactions of diseases other than the target disease of the study (cardiac amyloidosis, etc.)
- List of patients with liver transplant
- List of efficacy endpoints
  - NIS
  - QOL-DN
  - mBMI
  - Ambulatory status
  - Neurological assessment
  - Survival time
- List of medical evaluations of physical symptoms

In addition, the following tables corresponding to the attached forms will be prepared at the time of periodic safety update report and reexamination:

- Attached Form 1-2 (Status of occurrence of adverse reactions/infections up to the time of approval): Equivalent to Attached Form 2 for reexamination application materials
- Attached Form 2 (Status of occurrence of adverse reactions/infections in post-marketing surveillance, etc.): Attached Form 15 for reexamination application materials
- Attached Form 16 (List of outline of subjects)

## 10. Appendices

## 10.1. Appendix 1: Details of Data Extraction

If there are multiple records within the acceptable window, the record closer to the target visit will be adopted.

## A1.1 Definition of Visit Timing 1

Endpoint	Visit (target)	Definition [acceptable window]
NIS	Before the start of treatment	[Before the start of treatment
QOL-DN	(BL; Base line)	with this drug, Week 4]
Ambulatory status	Week 78	[Weeks 4, Week 104]
Medical assessment of	Week 156	(> Week 104, ∞]
physical symptoms		

## A1.2 Definition of Visit Timing 2

Endpoint	Visit (target)	Definition [acceptable window]
mBMI	Before the start of	[Before the start of treatment
	treatment (BL)	with this drug, Week 4]
	Week 26	[Week 4, Week 39]
	Week 52	[Week 40, Week 65]
	Week 78	[Week 66, Week 91]
	Week 104	[Week 92, Week 117]
	Week 130	[Week 118, Week 143]
	Week 156	[Week 144, Week 169]

## A1.3 Definition of Visit Timing 3

Endpoint	Visit (target)	Definition [acceptable window]	
Neurological assessment	Before the start of treatment (BL)	[Before the start of treatment with this drug, Week 4]	
	Week 52	[Week 4, Week 78]	
	Week 104	[Week 79, Week 130]	
	Week 156	[Week 131, Week 182]	

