7.3.2.8. Tests/clinical laboratory tests

For the following test items conducted from the first day of treatment with this drug until the end of the observation period (or date of discontinuation of treatment with this drug), enter the test dates (dates of measurement) and test results. For the tests conducted before the start of treatment with this drug, enter the test results immediately before the first day of treatment (including the first day of treatment). For clinically significant fluctuations compared to those before the start of treatment with this drug, enter the details in the adverse event column.

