7.3.2.8.5. Assessment of neurological function (NIS)

Enter scores for the following (1) to (4) items according to the assessment indicators for neurological function shown below by using Neuropathy Impairment Score $(NIS)^{9}$.

[Timing of assessment] Before the start of treatment (results immediately before treatment including the first day of treatment), Week 78 (1.5 years later), Week 156 (3 years later) (or at discontinuation of treatment with this drug)

(1) Cranial Nerves: Items 1 to 5(2) Muscle Weakness: Items 6 to 24

Cranial nerves and muscle weakness will be graded on the following 8-point scale: 0 = Normal 1 = 25% Weak 2 = 50% Weak 3 = 75% Weak 3.25 = Move against gravity 3.5 = Movement, gravity eliminated 3.75 = Muscle flicker, no movement 4 = Paralysis

(3) Reflexes: Items 25 to 29(4) Sensation: Index finger (items 30 to 33), great toe (items 34 to 37)

Tendon reflexes (reflexes) and sensation of index and great toes (sensation; tactile sense, pain sensation, vibration sense, joint sense) will be graded on the following 3-point scale: 0 = Normal

1 = Decreased

2 = Absent

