7.3.2.8.8. Neurological assessment

Enter the test results for the following neurological assessments (1) to (6). The observation period is defined as follows and, if the observation period is discontinued, enter the test results at the time of discontinuation as much as possible.

[Timing of assessment] Before the start of treatment (results immediately before treatment including the first day of treatment), Week 52 (1 year later), Week 104 (2 years later), Week 156 (3 years later) (or at discontinuation of treatment with this drug)

(1) Motor

The motor will be assessed using a Medical Research Council (MRC) Scale.

)	No contraction
1	Flicker contraction
2	Muscle contraction with active motion with gravity eliminated
3	Full range of motion against gravity
4	Full range of motion against gravity with some resistance
5	Full range of motion against gravity with maximum resistance for that muscle

(2) Reflexes

Reflexes will be assessed with the following items: Present, Absent

(3) Light Touch

- (4) Pin Prick
- (5) Vibration
- (6) Position Sense

Light touch, pin prick, vibration, and position sense will be assessed with the following scales: Normal, Decrease, and Absent

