## 10.2.2. Norfolk Quality of Life-Diabetic neuropathy (QOL-DN)

1	Symptoms	Numbness
2	Symptoms	Tingling sensation, prickling sensation with a pin, prickling
		sensation with a needle
3	Symptoms	Electrical sensation
4	Symptoms	Other abnormal sensations
5	Symptoms	Surface pain
6	Symptoms	Deep pain
7	Symptoms	Muscle weakness
8	Activities of daily living	During the past 4 weeks, have you had difficulty falling asleep at
		night due to pain?
9	Activities of daily living	During the past 4 weeks, have you felt painful to touch sheets or
		clothes or put on your shoes?
10	Activities of daily living	During the past 4 weeks, have you failed to feel any burns or
		injuries?
11	Activities of daily living	During the past 4 weeks, have you noticed any symptoms that
		interfered with your normal activities?
12	Activities of daily living	During the past 4 weeks, have you felt difficulty performing fine
		hand or finger tasks such as clicking on a button of clothing,
		flipping on a book page, or pinching a coin from a table?
13	Activities of daily living	During the past 4 weeks, have you noticed unsteadiness of your
		feet when walking?
14	Activities of daily living	During the past 4 weeks, have you had any problems with
		standing up from the chair without using your hands?
15	Activities of daily living	During the past 4 weeks, have you had problems going down
		stairs?
16	Activities of daily living	During the past 4 weeks, have you had no sensation in your feet
		while walking?
17	Activities of daily living	During the past 4 weeks, have you been unable to distinguish
		between hot and cold water by hand?
18	Activities of daily living	During the past 4 weeks, have you been unable to distinguish
		between hot and cold water by foot?
19	Activities of daily living	During the past 4 weeks, have you vomited particularly after
		meals (except vomiting associated with a cold or other illness)?
20	Activities of daily living	During the past 4 weeks, have you had diarrhea or problems with
		your intestines?
21	Activities of daily living	During the past 4 weeks, have you had fainting or dizziness when
		you stand up?
22	Activities of daily living	Bathing/showering?

23	Activities of daily living	Clothing?
24	Activities of daily living	Walking?
25	Activities of daily living	Sitting or standing from the toilet?
26	Activities of daily living	Using tableware?
27	Activities of daily living	Have you experience any reduction in the time of work or other activities?

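### SAP Appendix 1 lets a record taken up to Week 4 on treatment serve as baseline, against the pre-treatment definition in the protocol and SAP 6.2, and places Week 4 in two windows

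*SAP*

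**What the plan says.** The protocol fixes the baseline record for each efficacy measure. For NIS (7.3.2.8.5) it is "Before the start of treatment (results immediately before treatment including the first day of treatment"; QOL-DN (7.3.2.8.6) and ambulatory status (7.3.2.8.7) follow the same rule, and the neurological assessment (7.3.2.8.8) has "Before the start of treatment (results immediately before treatment including the first day of treatment), Week 52 (1 year later". For tests and laboratory values, which supply the weight and albumin for mBMI, sites must "enter the test results immediately before the first day of treatment (including the first day of treatment" (7.3.2.8).

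SAP 6.2 also describes baseline as preceding the start of treatment. SAP 8.2.4.1 to 8.2.4.3 and 8.2.4.5 express every change as a change from before treatment.

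SAP Appendix 1, which governs data extraction, differs. In A1.1, A1.2 and A1.3 the baseline window is "Before the start of treatment with this drug, Week 4", with Week 4 included. The first post-baseline window in A1.1 (target Week 78) is "Weeks 4, Week 104", again with both ends included. A1.2 and A1.3 also open their first post-baseline window at Week 4. The only selection rule is "If there are multiple records within the acceptable window, the record closer to the target visit will be adopted".

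**The concern.** Change from baseline is the main planned summary for NIS, QOL-DN and mBMI (Protocol 7.7). Baseline total NIS, NIS-LL and TQOL also define subgroups (SAP 5.4). There is no control group, so nothing offsets a misplaced starting point.

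The window rule creates two problems. First, a value recorded after up to four weeks on drug can be tabulated as the pre-treatment value, and any change before that record drops out of the summary. Second, one Week 4 record satisfies both the baseline window and the next one. If it fills both, the patient contributes a change of zero that reflects no follow-up. In the ambulatory shift table (SAP 8.2.4.4) it becomes a false unchanged cell.

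**Working it through.** The documents give no count or effect figure on this point, so there is nothing to reproduce. The check sets the windows side by side and applies the selection rule to example records.

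**Windows as printed (SAP Appendix 1)**

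| Table | Endpoints | Baseline ends | First post-baseline window | Following window starts |
|---|---|---|---|---|
| A1.1 | NIS, QOL-DN, ambulatory status, physical symptoms | Week 4, included | Target 78: Weeks 4 to 104, both included | after Week 104 |
| A1.2 | mBMI | Week 4, included | Target 26: Weeks 4 to 39, both included | Week 40 |
| A1.3 | Neurological assessment | Week 4, included | Target 52: Weeks 4 to 78, both included | Week 79 |

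In each table, on-treatment Weeks 1 to 4 qualify as baseline, and Week 4 is the only week in two windows. The later boundaries do not overlap, so the shared Week 4 looks unintended. The selection rule chooses among several records in one window. It does not assign a record that lies in two windows, and it does not rank pre-dose records first.

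**Example records under A1.1.** Assumption: the baseline target is the first day of treatment, week 0. The SAP names the target only as before treatment and does not say how distance to it is measured.

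| Records (week) | Baseline chosen | Week 78 value | Result |
|---|---|---|---|
| 4 only | 4 | 4 | same record twice, change = 0 |
| 2, 76 | 2 | 76 | on-drug baseline |
| -20, 2, 60 | 2 (distance 2, against 20) | 60 | pre-dose record displaced |
| -1, 4 | -1 | 4 | no forced zero |
| 4, 30 | 4 | 30 | on-drug baseline, no forced zero |

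The first row gives a zero change under A1.2 and A1.3 too. The last two rows show how narrow that case is: an earlier record nearer the start displaces Week 4 as baseline, and a later record nearer the target displaces it as the follow-up value.

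**Size for an affected patient.** Assume linear change with slope s, follow-up at target week T and baseline taken at week b. The full change is s × T and the measured change is s × (T − b), so the share lost is b/T.

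- b = 4, T = 78: 4/78 = 5.1%
- b = 4, T = 156: 4/156 = 2.6%
- b = 4, T = 26 (mBMI): 4/26 = 15.4%
- b = 2: 2/78 = 2.6% and 2/26 = 7.7%

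The b = 4 figures are maxima over the baseline window for follow-up on target. A follow-up record earlier in its window loses a larger share. The limit is the doubly used Week 4 record, 4/4 = 100%, which is the forced zero.

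**QOL-DN recall.** In SAP 10.2.2, items 8 to 21 (14 items) and 33 to 35 (3 items) state a four-week recall, for example "During the past 4 weeks, have you had difficulty falling asleep". That is 17 of 35. For these items a Week 4 answer describes essentially on-treatment time.

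**The case against.** The strongest reply is that the exposure is small. The baseline target is labelled as before treatment, so a pre-dose record may be meant to win, with Day 2 to Week 4 only a fallback for missing data. Sites are told to enter pre-dose results. NIS and QOL-DN are scheduled only before treatment, at Weeks 78 and 156 and at discontinuation, so stray early records should be uncommon. Protocol 7.7 lets the SAP modify the protocol's plans, and the survey is descriptive, with no hypotheses or decision rules (SAP 4.1, 4.2).

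Much of this limits the size, but it does not remove the defect. The fallback reading is reasonable but unwritten. Permission to modify does not reconcile Appendix 1 with SAP 6.2 and 8.2.4, which still say baseline comes before treatment. mBMI is the most exposed measure, because weight and albumin results are collected throughout observation. Protocol 7.3.1 restarts the first day of treatment for patients coming from clinical studies or other sites, so some baselines are on-drug under any window. That is no reason to add more.

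A reader might infer three stronger points, and the documents support none of them:

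- **That the rule pushes results towards no progression.** This assumes early change is worsening. Protocol section 5 reports improved nutritional condition in overseas studies. If mBMI rises early, a late baseline absorbs the gain and later change looks worse.
- **That late first assessments are likely because data come from charts.** Protocol 7.9 says data may be missing, not that they are late.
- **That a Week 4 QOL-DN baseline reflects only treated time.** Only 17 of 35 items state a four-week recall, and item 32 compares with three months earlier, which at Week 4 reaches back before the first dose.

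**Conclusion.** The point holds as an inconsistency with a bounded consequence. The baseline windows in A1.1 to A1.3 contradict the protocol and the SAP's own text, and Week 4 belongs to two windows in every table. Following the SAP literally can report an on-drug value as pre-treatment. If distance is measured from the first day of treatment, that value can even displace an earlier pre-dose record. The exact zero is confined to patients whose Week 4 record is both the chosen baseline and the only record in the next window, for example some early discontinuers.

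The percentages above are per affected patient and rest on linear change with follow-up on target. The effect on the summary means cannot be computed, because the number of affected patients is not given, and its direction is not fixed. The correction is worth making because it is specific and cheap, but the documents do not show that the efficacy results are materially distorted.

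**What to change.** In SAP Appendix 1:

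1. Define baseline in all three tables as the last record on or before the first day of treatment, as the protocol does.
2. Open the first post-baseline window strictly after Week 4 (> Week 4) in A1.1, A1.2 and A1.3, so that no record falls in two windows. It should not open straight after the first dose: in A1.1 a Day 2 record could then stand as the Week 78 value for a patient who stops early, giving a near-zero change.
3. Show patients whose only early record is from Day 2 to Week 4 in a labelled sensitivity analysis that uses that record as baseline, and report how many there are.

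Applied to the examples, records at weeks -20, 2 and 60 give baseline -20, and a lone Week 4 record gives no change instead of a zero.

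The cost is SAP wording and extraction logic, with no new data. Patients without a pre-dose record leave the main change summary, and a patient whose only record in the first post-baseline window is at exactly Week 4 loses that visit's value.
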